### OBJECTIVES

As part of the Precision Health initiative at the University of Michigan, this project is focused on the effects of wearable and mobile technology to both reduce mental health symptoms and predict response to clinic-based treatments.

The overall goal of this project is to reduce the burden of mental health conditions by two means:

- 1) Increasing capacity in the mental health care system through expanding use of mobile technology-delivered interventions.
- 2) Accelerating recovery by matching patients to the pharmacological, psychological, and mobile-based treatments from which they will likely derive the greatest benefit.

To do so, we will complete the following **specific aims**:

**Aim 1:** To assess the independent and combined effectiveness of two classes of mobile technology interventions among patients while on the waitlist for traditional care:

- (a) App-based cognitive behavioral and mindfulness interventions
- (b) Enhanced objective, mobile data feedback on mood, sleep, heart rate, and activity levels

**Aim 2:** To use machine learning to identify key predictors of treatment response from mobile technology,

genomic, and environmental data collected from patients receiving:

- (a) Mobile technology interventions while on a waitlist for outpatient mental health care
- (b) Traditional face-to-face psychotherapy, medication, or neuromodulation treatment

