## **RESEARCH DESIGN AND METHODS**

This study will have **two phases**, each with different study designs:

**Phase 1** will cover the period while individuals are waiting for care. The design of this phase is a randomized clinical trial, wherein participants are randomly assigned to one of three study conditions that vary by the type of Mobile Health (mHealth) intervention they can receive.

**Phase 2** begins when a participant has a first appointment for outpatient mental health care, and uses a cohort study design for measuring outcomes associated with clinic-based treatments.

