### Surveys

Participants will be asked to complete four surveys, including a baseline survey at the time of enrollment and three follow-up surveys, which will be designed to complement in-clinic assessments completed as a part of standard outpatient mental health care. To the extent possible, redundancy with in-clinic assessments (i.e., due to the Measurement-Based Care program) will be avoided. The first follow-up survey will occur at the end of 6 weeks post-enrollment, the second at the end of 18 weeks post-enrollment and the third at the end of 12 months post-enrollment.

Depending on waitlist length for outpatient mental health services, there may be variation in whether participants have engaged with clinical care by the time they complete their follow-up survey(s). Surveys will be administered by the predetermined schedule regardless of whether participants have engaged with care. The rationale for this decision, rather than scheduling follow-up surveys to coincide with the initiation of outpatient care:

1. There is a possibility that participants may never engage with outpatient care, and these non-engagers would never receive follow-up surveys
2. Waitlist time often varies between recruitment sites (i.e., UHS tends to have a shorter waitlist for care), which would create measurement biases (e.g., UHS patients may consistently engage in care with less time to engage with the app-based intervention)
3. Participants may be receiving other mental health care (e.g., via primary care), making it less important to time follow-up surveys with the initiation of outpatient mental health services
4. The existing timeline ensures all participants randomized to the groups receiving app-based interventions have received a reasonable 'dose' of the intervention prior to assessment
5. The existing timeline ensures that measurement will take place at generally the same time frame for all participants

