### ***Self-Report Surveys***

Participants will complete four surveys, including a baseline survey and three follow-up surveys. All surveys will be self-administered via the MyDataHelps study app. In the case of technological difficulties, the study team does have paper copies of the baseline and follow-up surveys available, and the surveys may be administered in person or by phone. The baseline survey will take about 25 minutes. Survey questions include demographics, overall physical and mental health symptoms and diagnoses, substance use, environment, use of mobile technology and health apps, and social network and support. For each of the three follow-up assessments, participants will complete an approximate 20-minute survey with similar content as the baseline survey. If necessary, the survey can be administered by study staff via phone who will read survey questions to the participant and record their responses. When participants are due for their surveys, they will receive an email or app notification that their survey is available via the MyDataHelps app. If participants do not respond to the questionnaires, and have not indicated that they do not wish to participate in the study, a reminder will be sent by email, phone, mail, or text message.

The first follow-up survey will occur at the end of 6 weeks post-enrollment, the second at the end of 18 weeks post-enrollment, and the third at the end of 12 months post-enrollment. Each of these time-points may occur near the time of an in-person outpatient mental health clinic appointment, at which participants may be asked to answer some of the same questions that are contained in the study surveys. To reduce participant burden, study staff will monitor upcoming appointments and participants will receive a version of the survey without redundant items if they have an appointment within 1 week of their follow-up survey due date. They will still complete the remainder of the follow-up survey and be paid the same amount for their time. Additionally, participants who do not show for clinic appointments will still be able to complete the follow-up assessments via standard study procedure.

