### ***Biological Specimen***

A biological specimen will be obtained as part of this study, which will be facilitated by the University of Michigan Medical School Central Biorepository (CBR). The CBR will facilitate ordering of DNA collection kits, as well as the processing and storage of DNA samples. The Michigan Genomics Initiative (MGI) (HUM00071298) is a collaborator in this study, and MGI will cover the costs of DNA collection kits, processing, and storage that are charged by the CBR. Participants that have previously participated in MGI will not receive genetic analyses as part of this protocol, given that their biological specimen has already been submitted to the CBR.

Participants will be sent DNA collection kits via postal mail and asked to provide a small sample of saliva. Participants will return samples to study team members in a provided self-addressed, stamped return envelope. Participants also have the option to provide a saliva sample in person, if needed or preferred.

Genetic analyses will be carried out on the DNA sample. Incidental findings from the DNA analysis will not be shared with the participant or the participant's physician.

If participants do not submit a DNA sample and have not indicated that they do not wish to participate in the study, they will be contacted by a study team member by phone, email, text message, or mail as a reminder. Study staff will be trained to discuss confidentiality and privacy of genetic data to improve participant adherence with the request to submit a DNA sample.

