### **ANALYSIS PLAN**

A primary goal is to obtain information about the feasibility and acceptability of the use of app-based interventions and enhanced feedback in response to mobile health device use, as well as to estimate the distribution and variability of potential primary and secondary outcomes of interest. Data will be examined using standard univariate summary measures, bivariate statistical tests of association, and graphical displays. We will assess subjective and objective data in areas including mental health and physical health measures, substance use, and app use. This will assess responsiveness to the interventions as well as how best to provide clinicians with useful patient data that may help inform treatment decisions. This is a primary outcome for future work. Additional outcomes to be assessed are listed in Table 1.

We will calculate means and standard deviations for participant characteristics and outcomes measures at each assessment and also for change scores. With outcomes that are categorical, we will use the Chi square test, and with outcomes that are continuous, we will use t-tests to make comparisons.

We will also conduct baseline and ongoing analyses of the presence of genotype x stress interaction among this sample. For example, as a baseline analysis, we will investigate association between each variant/haplotype and PHQ (baseline) scores using linear regression. To explore gene x environment interactions, we will assess for association between each variant/haplotype and PHQ (change) scores.

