**Table 1: Study Measures and Administration Time Points**

Measure	Areas of Assessment	Administration Schedule
Demographics	Age, Sex, Race, Ethnicity, Education, Housing, Income	Baseline
Zip Code (Current or Permanent Address)	Social Determinants of Health	Baseline
Risky Families Questionnaire	Early Family Environment	Baseline
NEO-Five Factor Inventory (Select items - Neuroticism Items)	Neuroticism (Domain of Personality)	Baseline
Pittsburgh Sleep Quality Index	Sleep Quality And Disturbance	Baseline
Mental Health Symptom Assessment	Mood Self-Report	Daily
Brief Suicide Risk Measure (Czyz, et al., 2016)	Suicide Risk	Weekly
Mental Health App Assessment Questions - (Adapted from Kern, et al., 2018)	Frequency of Use of Mental Health, Physical Activity, and Mindfulness Apps	Baseline 6 weeks 18 weeks 12 months
Patient Health Questionnaire (PHQ-9)	Depression	Baseline 6 weeks 18 weeks 12 months
Positive and Negative Suicide Ideation Inventory (PANSI)	Suicide Risk Assessment	Baseline 6 weeks 18 weeks 12 months

Generalized Anxiety Disorder 7-Item Scale (GAD-7)	Anxiety	Baseline 6 weeks 18 weeks 12 months
Posttraumatic Stress Disorder Checklist (PCL-5) with PC-PTSD stem question	Post-Traumatic Stress Disorder	Baseline 6 weeks 18 weeks 12 months
Alcohol, Smoking, and Substance Involvement Screening Test (ASSIST)	Substance Use (excluding opioid use)	Baseline 6 weeks 18 weeks 12 months
Current Opioid Misuse Measure (COMM)	Opioid Misuse	Baseline 6 weeks 18 weeks 12 months
Interpersonal Support Evaluation List (ISEL-12)	Brief Social Support Inventory	Baseline 6 weeks 18 weeks 12 months
Satisfaction and Engagement with Care	Self-reported satisfaction with care and reasons for no-shows	18 weeks
Numerical Rating Pain Intensity Scale (NRS)	Pain	Baseline 6 weeks 18 weeks 12 months

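### The gene-by-environment test contains no exposure, so it cannot separate an interaction from a genotype effect on symptom change

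*Combined protocol and SAP*

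**What the plan says.** The genetic work is described at the end of the Analysis Plan. Its target is an interaction: "We will also conduct baseline and ongoing analyses of the presence of genotype x stress interaction among this sample". Two analyses follow. The first regresses baseline PHQ on each variant or haplotype. The second is the gene-by-environment analysis: "To explore gene x environment interactions, we will assess for association between each variant/haplotype and PHQ (change) scores". Neither sentence includes an exposure measure, a product term or a stratification, and the follow-up visit for the change score is not named. Table 1 schedules the PHQ-9 at baseline, 6 weeks, 18 weeks and 12 months.

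The study does collect possible exposures. According to the section on self-report surveys, the questions cover "overall physical and mental health symptoms and diagnoses, substance use, environment, use of mobile technology and health apps". Table 1 lists the Risky Families Questionnaire (early family environment), zip code (social determinants of health) and the ISEL-12 (social support). None of these is assigned to the genetic analysis, and no measure is designated as the stress exposure. The entry "Posttraumatic Stress Disorder Checklist (PCL-5) with PC-PTSD stem question" has stress in its name but is listed as assessing post-traumatic stress disorder.

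**The concern.** An interaction between genotype and environment means that the genotype effect differs by level of exposure. A regression of change on genotype alone does not address that, because exposure is not in the model.

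A change score can stand in for an interaction test when everyone passes through the same stressor between the two measurements. That is not the design here. Under Research Design and Methods, "participants are randomly assigned to one of three study conditions that vary by the type of Mobile Health (mHealth) intervention they can receive", and the Surveys section accepts that participants will differ in whether they have started clinical care by the time of a follow-up survey. An association between genotype and change could therefore reflect natural course or response to treatment as readily as sensitivity to stress.

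Two errors become possible. A variant that predicts symptom course or treatment response could be read as gene-by-environment, and a real interaction that averages to zero over the sample could be missed.

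**Working it through.** The documents give no effect size, significance threshold, allele frequency or number genotyped for this analysis, so there is no figure of the plan's own to reproduce. The main result is algebraic; the numbers after it are illustrations.

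**Algebra.** Let G be the allele count, E the exposure, and change = a + bE·E + bG·G + bGE·G·E + noise. If G and E are independent, the slope from regressing change on G alone is

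slope = bG + bGE·mean(E).

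One estimate cannot separate bG from bGE. If G and E are correlated, the exposure main effect bE also enters the slope.

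**Inputs.** From the documents: N = 4,500, the recruitment target. Assumed: N = 2,000 as an alternative; allele frequency 0.3, so Var(G) = 2 × 0.3 × 0.7 = 0.42; binary exposure in 50%, so Var(E) = 0.25; bE = 0.2; noise SD 1; two-sided thresholds of 5% and 5e-8. There were 2,000 simulation runs per setting.

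**Three scenarios and the slope each gives the stated test**
- A, genotype effect on change, no interaction: 0.10 + 0 × 0.5 = 0.10
- B, interaction only, 0.20 SD in the exposed: 0 + 0.20 × 0.5 = 0.10
- C, −0.10 SD unexposed and +0.10 SD exposed: −0.10 + 0.20 × 0.5 = 0

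A and B look identical to the stated test, and C looks like no effect.

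**Rejection rates, stated test / product term**

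| N, threshold | A | B | C |
|---|---|---|---|
| 4,500, 5% | 99% / 5% | 99% / 99% | 5% / 99% |
| 2,000, 5% | 82% / 5% | 80% / 81% | 6% / 81% |
| 4,500, 5e-8 | 12% / 0% | 12% / 14% | 0% / 12% |
| 2,000, 5e-8 | under 1% | under 1% | under 1% |

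With no genotype effect and no interaction, both tests reject about 5% of the time at the 5% threshold.

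**Closed-form check, stated test in A.** The residual SD with E omitted is √(1 + 0.2² × 0.25) = 1.005, so SE = 1.005/√(N × 0.42). At N = 4,500, z = 4.33 and power is 99.1% at 5% and 13.0% at 5e-8. At N = 2,000, z = 2.88 and power is 82.2% and 0.5%. These agree with the simulation.

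**Smaller effects** (N = 4,500, 5% threshold). With half the effect sizes (0.05 SD): A 57% / 5%, C 5% / 58%. With 0.02 SD: A 14% / 5%, C 5% / 14%.

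**Dependence on the exposure mean.** With a continuous exposure, bG = 0 and bGE = 0.1 (N = 4,500, 5% threshold), the stated test rejects in 6%, 55% and 99% of runs when the exposure mean is 0, 0.5 and 1 SD. The product term rejects in 99% to 100% each time.

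**Correlated G and E.** With bG = bGE = 0, the slope is bE·r/SD(G) = 0.2 × 0.1/0.648 = 0.031 at correlation 0.1. At N = 4,500 and 5%, the rates are 26% / 5% at correlation 0.1 and 76% / 5% at 0.2. At 5e-8 all are 0.2% or less.

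**What is not affected.** A genotype effect on symptom level that is constant over time cancels in the change score. With an effect of 0.1 SD on level (baseline to follow-up correlation 0.5, N = 4,500), the stated test rejects in 6% of runs at the 5% threshold.

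**The case against.** The strongest reply concerns framing and weight. The genetic paragraph introduces its baseline analysis as an example and calls the gene-by-environment work exploratory, so other models are not excluded. It does name stress as the construct; what it lacks is a measure and a model term. It does not say how an association will be labelled in a report. Aim 2 separately plans machine learning on "genomic, and environmental data collected from patients receiving" the mobile interventions or clinic-based care.

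The high rejection rates also depend on favourable assumptions. An effect of 0.10 SD per allele is about 0.42 × 0.01 = 0.42% of the change-score variance from one variant. A single 5% test is not the natural setting when every variant or haplotype is examined. The number genotyped may fall short of 4,500, since the section on biological specimens provides reminders for participants who return no sample ("If participants do not submit a DNA sample and have not indicated that they do not wish to participate in the study").

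Much of this stands as a limit on size. Misreading a result as gene-by-environment is a possibility, not a certainty, and the 99% figures belong to one favourable setting. The core is unaffected. The example wording attaches to the baseline analysis, while the gene-by-environment sentence directly states what will be done and is the only such test written down. Aim 2 concerns prediction of treatment response and states no genotype-by-stress test.

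**Conclusion.** The concern holds. The stated test does not answer the question set for it, because its slope mixes a genotype effect on change with the interaction. That conclusion needs no assumed effect size. How often it would mislead does depend on assumptions: from 99% for a 0.10 SD effect in one 5% test at 4,500 participants, through 14% for a 0.02 SD effect in the same setting, to under 1% for the 0.10 SD effect at 5e-8 with 2,000 participants. The consequence is confined to an exploratory genetic analysis. Aim 1 and the randomised comparison are not touched, so this is an improvement worth making and not a condition for the trial.

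**What to change.** Rewrite the gene-by-environment sentence so that it names the exposure, the PHQ-9 time point and the significance threshold. Fit genotype, exposure and their product, and base any gene-by-environment conclusion on the product term.

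One workable pairing, offered as a design choice:
- For an exposure that predates enrolment, such as the Risky Families Questionnaire, use baseline PHQ-9 as the outcome, because the interaction may already be present by then.
- For a possible modifier of course, such as baseline ISEL-12 or a zip-code measure, use PHQ-9 change to one named visit.

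Keep the present regression if wanted, but call it *genetic predictors of symptom change*. If genotype by randomised group is tested, call it *genotype x treatment*, not genotype x stress. If no collected measure suits as the stress exposure, restate the target as gene by the named exposure.

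The cost is one paragraph of wording. No new data are needed if the target is restated in that way, since the measures are already in Table 1, and relabelling alone would cure the naming problem. The drawback is low power for interaction at strict thresholds: under the assumed effects, about 12% to 14% at 5e-8 with 4,500 participants and under 1% with 2,000. The present test has the same limit for its own assumed effect (12% and under 1%).

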### **POTENTIAL RISKS, MINIMIZING RISKS, AND POTENTIAL BENEFITS**

#### **Potential Risks and Minimizing Risks**

##### **Breach of confidentiality (Rare likelihood of risk)**

Several measures have been taken to reduce the risk of breach of confidentiality. These include training of study team members, electronic and physical security measures for data capture and storage, and collecting a minimum of identifiable information for each individual participant. The study will also pursue a Certificate of Confidentiality, pending IRB approval. Unique identification (ID) numbers will be assigned to all participants who complete the assessments. All data forms and assessments will be coded with this number rather than with participants' names. Breach of confidentiality will be considered a "definitely related" Serious Adverse Event. As such, it will be reported to the University of Michigan IRB within 7 days of occurrence, and a remediation plan will be put in place immediately.

**Collection and storage of biospecimens (Rare likelihood of risk)**

Saliva collection kits will be mailed to participants who will self-collect saliva by spitting in a coded tube and returning in a pre-addressed, stamped envelope with no participant identifiers. DNA will be stored in a coded manner for future testing and be linked to other phenotyping data only by anonymous Participant ID number. There is a rare risk of jaw and cheek tiredness, soreness, and pain, as well as dry mouth associated with producing a DNA saliva sample.

**Failure to follow safety instructions of the study devices (Rare likelihood of risk)**

Participants will be encouraged to review the Apple Watch or Fitbit User Guides before using Apple Watches or Fitbits for the study.

**Risk from wearing the Apple Watch or Fitbit (Rare likelihood of risk)**

A small number of people may experience reactions to certain materials. This can be due to allergies, environmental factors, extended exposure to irritants like soap or sweat, or other causes. Participants are advised to remove their Apple Watch or Fitbit and consult their physician if they experience redness, swelling, itchiness, or any other irritation.

**Discomfort associated with being asked personal questions about health history and the completion of questionnaires (Infrequent likelihood of risk)**

There is also the risk of psychological discomfort by study participants from questions asked in the assessments. Any participant becoming distressed while completing questionnaires will be encouraged to seek clarification of questions that they find to be unclear or troubling. The participant may skip any question that they find distressing. All participants are told that they have the option to terminate participation without penalty. Research staff will be trained to discuss any issues or concerns if they arise and will assist in arranging medical/psychiatric help if necessary, including emergency treatment.

**Discomfort associated with being asked questions about suicidal ideation and engaging in risk assessments (Likely risk)**

There is the risk of psychological discomfort or stress by study participants surrounding questions being asked in the assessments about suicide and risk. Participants may experience some emotional discomfort or stress from discussing or answering these questions, including when being engaged in as-indicated risk assessments. The research staff conducting the assessments will be trained to respond to this emotional discomfort or stress and refer participants to appropriate resources as necessary, including supervisory backup within the research team. The Investigators or Project Manager will conduct face-to-face trainings with research staff to comprehensively review the Risk Management Protocol, risk factors for suicide, and techniques to distinguish low-, moderate-, and high-risk participants. In addition, the Investigators and Project Manager will monitor the progress of the study and quality of the assessments, and conduct additional ongoing in-person training and re-training as necessary over the course of the study. In order to ensure participant safety, there is the rare likelihood of the need for breach of confidentiality if research staff or investigators determine that a participant is at significant risk of suicidal or homicidal crisis or if there is mention of child or elder abuse.

